4.3.1.3. Dose Proportionality

The following pharmacokinetic statistical analyses will only be performed if sufficient data are available (i.e., if more than 5 subjects have well defined plasma profiles). If the dose with limited data is at the lower end of the dose range, the data will be excluded, and the appropriate analysis conducted on the rest of the data. However, if there are non-calculable PK parameter data at intermittent doses no statistical analyses will be performed. The assessment of dose proportionality will utilise Period 1,2 and the first dose of Period 3 data only.

Dose proportionality will be assessed using power method as primary, and ANOVA as supportive method:

Pharmacokinetic Statistical Analyses for Dose Proportionality: Power Method
Endpoint(s)

 AUC(0-6), Cmax Each endpoint to be assessed separately.
Model Specification

 $\log_e(Y) = \beta \times \log_e(\text{dose}) + \log_e(\alpha)$ where Y is the pharmacokinetic parameter and $\log_e(\alpha)$ is an intercept term.
Model Results Presentation

 The coefficient of the slope with 90% confidence intervals, on the log scale, will be calculated, using the pooled estimate of variance, and used to assess dose proportionality. Point estimates and confidence intervals for the slope will be reported to 2 decimal places

Pharmacokinetic Statistical Analyses for Dose Proportionality: ANOVA Method
Endpoint(s)

 AUC(0-6), Cmax Each endpoint to be assessed separately.
Model Specification

 The PK parameter will be dose-normalised prior to loge-transformation by multiplying by reference dose / dose Dose will be fitted as a fixed effect, subject as a random effect using DDFM=KR. The reference dose will be chosen based on the lowest clinically relevant dose over which PK can be adequately described, with each other dose as the test doses in the construction of the ratio $\mu(\text{test})/\mu(\text{reference})$.
Model Results Presentation

Pharmacokinetic Statistical Analyses for Dose Proportionality: ANOVA Method

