4.3.1.5. Model Checking Diagnostics

Model checking diagnostics for dose proportionality and dose accumulation analysis will include the following:

- The Kenward and Roger method for approximating the denominator degrees of freedom and correcting for bias in the estimated variance-covariance of the fixed effects will be used.
- An unstructured covariance structure for the R matrix will be used by specifying

'type=UN' on the REPEATED line.

- In the event that this model fails to converge, alternative correlation structures may be considered such as CSH or CS.
- Akaike's Information Criteria (AIC) will be used to assist with the selection of covariance structure.
- Distributional assumptions underlying the model used for analysis will be examined by obtaining a normal probability plot of the residuals and a plot of the residuals versus the fitted values (i.e., checking the normality assumption and constant variance assumption of the model respectively) to gain confidence that the model assumptions are reasonable.

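### The SAP gives the primary power-model slope two incompatible variance rules: one pooled variance with no subject term (4.3.1.3), and Kenward-Roger with an unstructured R matrix (4.3.1.5)

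*SAP*

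**What the plan says.** SAP 4.3.1.3 ranks the methods: "Dose proportionality will be assessed using power method as primary, and ANOVA as supportive method". The data are up to three first-dose profiles per participant: "The assessment of dose proportionality will utilise Period 1,2 and the first dose of Period 3 data only".

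- **Power model (primary).** The specification regresses log(Y) on log(dose) with an intercept. It names no subject term, random effect or covariance structure. For the interval it says: "The coefficient of the slope with 90% confidence intervals, on the log scale, will be calculated, using the pooled estimate of variance". What is pooled is not defined.
- **ANOVA (supportive, same data).** "Dose will be fitted as a fixed effect, subject as a random effect using DDFM=KR". The accumulation model in SAP 4.3.1.4 likewise states a random subject and Kenward-Roger.
- **SAP 4.3.1.5.** "Model checking diagnostics for dose proportionality and dose accumulation analysis will include the following". The list asks for "The Kenward and Roger method for approximating the denominator degrees of freedom and correcting for bias" and then: "An unstructured covariance structure for the R matrix will be used by specifying" type=UN on the REPEATED line. The fallback is: "In the event that this model fails to converge, alternative correlation structures may be considered such as CSH or CS", with AIC helping the choice. The power model is not exempted.

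**The concern.** The slope and its 90% interval are the primary dose-proportionality result. Read alone, 4.3.1.3 describes ordinary least squares, with repeated values from one person treated as independent. Read with 4.3.1.5, it describes a slope with a separate variance at each dose and a covariance for each pair of doses. One pooled variance and an unstructured R matrix cannot both hold, so two programmers could follow the SAP faithfully and report different primary intervals.

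The literal reading also leaves between-subject differences in the error term, although Protocol 4.1 gives reduced impact of inter-individual variability as a reason for the crossover. If subjects differ mainly in overall exposure, the interval is too wide and contains 1 too readily, so a departure from proportionality is harder to see.

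**Working it through.** **Inputs.** Sequences APA, AAP, AAA and PAA, three participants each, come from the sequence table in Protocol 4.1 and SAP 1.2. The doses are 500, 1000 and 1500 mcg (Protocol 4.1). Completers number 8 to 12 (SAP 5). The PK confidence level is 90% (SAP 4.1.1). The SAP states no figure for the slope interval, so there is none to reproduce.

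**Observations.** With 12 completers, nine give two active profiles and three give three: 9×2 + 3×3 = 27. With 8, assuming two per sequence: 6×2 + 2×3 = 18. Least-squares df are 27 − 2 = 25 or 18 − 2 = 16. With subject as a fixed effect they are 27 − 12 − 1 = 14 or 18 − 8 − 1 = 9.

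**Closed form, 12 completers, level differences only.** Let ρ be the ICC (between-subject share of intercept-plus-residual log-variance σ²).

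- Centred log doses are −0.597, 0.096 and 0.501, so Sxx = 9 × (0.597² + 0.096² + 0.501²) ≈ 5.56.
- The squared subject totals of centred log dose sum to Sxx/3. The true variance of the least-squares slope is therefore (σ²/Sxx)(1 − ρ + ρ/3) = (σ²/Sxx)(1 − 2ρ/3).
- The expected pooled variance is σ²[25(1 − ρ) + 24.33ρ]/25 = σ²(1 − 0.0267ρ).
- True SE over nominal SE is √[(1 − 2ρ/3)/(1 − 0.0267ρ)]. At ρ = 0.5 this is √(0.667/0.987) = 0.82; at ρ = 0.9, √(0.400/0.976) = 0.64.
- The within-subject share of Sxx is 5/6, so the within-subject slope variance is 1.2(1 − ρ)σ²/Sxx. The approximate width ratio, literal to within-subject, is (1.708/1.761) × √[(1 − 0.0267ρ)/(1.2(1 − ρ))], using the t quantiles on 25 and 14 df. At ρ = 0.5 this gives 0.970 × √(0.987/0.600) = 1.24.

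**Simulation, literal reading, level differences only** (true slope 1; 40,000 runs per cell, and 6,000 for the Kenward-Roger column; cells show 12 / 8 completers):

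| ICC | Coverage of literal 90% CI, % | Width ÷ within-subject CI | Width ÷ random-intercept Kenward-Roger CI |
|---|---|---|---|
| 0 | 90.1 / 90.3 | 0.89 / 0.88 | 1.02 / 1.02 |
| 0.1 | 90.8 / 91.1 | 0.94 / 0.92 | 1.04 / 1.04 |
| 0.3 | 93.0 / 92.8 | 1.06 / 1.04 | 1.13 / 1.12 |
| 0.5 | 95.1 / 94.7 | 1.25 / 1.23 | 1.29 / 1.27 |
| 0.7 | 97.1 / 96.9 | 1.60 / 1.57 | 1.63 / 1.60 |
| 0.9 | 99.0 / 99.0 | 2.75 / 2.70 | 2.77 / 2.71 |

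The mean least-squares slope was 0.997–1.002, so it is unbiased. The within-subject interval covered 89.6–90.3%. The random-intercept Kenward-Roger interval covered 88.9–90.1% with 12 completers and 88.0–90.2% with 8.

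**Simulation, unstructured R with Kenward-Roger, level differences only** (six covariance parameters; 3,000 runs per cell; ICC 0/0.3/0.5/0.7/0.9). With 12 completers, REML reached a positive-definite solution in 77–80% of datasets. Among those, coverage was 86.9/85.9/86.8/85.9/85.4%, and the literal interval was 0.91/1.01/1.16/1.44/2.46 times as wide (ratio of medians). With 8 completers a solution was reached in 34–37%, with coverage 88.7–89.2% and width ratios 0.83/0.92/1.03/1.27/2.15. Convergence rates depend on the algorithm. In a smaller run with a different optimiser (200 trials per setting, 12 completers), the literal and unstructured intervals differed at the two reported decimals in every usable fit.

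**Simulation, subjects also differ in slope** (12 completers; the multiple is slope variance ÷ σ²):

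| ICC | Multiple | Literal coverage, % | Random-intercept Kenward-Roger coverage, % |
|---|---|---|---|
| 0.3 | 1 | 88.7 | 86.1 |
| 0.5 | 0.25 | 93.2 | 88.1 |
| 0.5 | 0.5 | 92.1 | 87.1 |
| 0.5 | 1 | 90.3 | 85.4 |
| 0.7 | 0.25 | 95.8 | 87.5 |
| 0.7 | 0.5 | 94.2 | 85.9 |
| 0.7 | 1 | 91.8 | 84.0 |

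With slope differences but no level differences (within-subject SD 0.2), literal coverage falls to 82.3% at slope SD 0.3 and 75.4% at slope SD 0.6.

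**The case against.** The best defence is that 4.3.1.3 gives only the mean model and 4.3.1.5 supplies covariance and degrees of freedom. Section 4.3.1.5 names dose proportionality, an unstructured R matrix makes sense only with repeated values per subject, and the word pooled is undefined. This reading is possible, but the SAP does not state it, and pooled fits an unstructured matrix poorly. It also leads to six covariance parameters in an incomplete design with 12 subjects.

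Second, the unstructured results above exclude non-converged datasets, where the SAP would allow CSH or CS. For non-negative correlation, CS with Kenward-Roger is the same marginal model as a random intercept. So the SAP might sometimes arrive at the model recommended here. That stands as a limit on those figures. It also means the primary interval would depend on convergence and on a fallback that is only permitted.

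Third, the recommended model is not better calibrated everywhere. In all seven cells with slope differences it falls below 90%, and the literal interval is nearer nominal in four of them and about level in a fifth. This stands. The literal interval does well there because two errors offset: it ignores level differences, which widens it, and slope differences, which narrow it. That balance cannot be relied on.

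Fourth, the consequences are small. SAP 2 plans no hypothesis test, the slope has no acceptance bound, and the supportive ANOVA keeps within-subject precision. The 8-completer layout is also a simplification, because the PK set does not require completion. All of this is accepted and limits the weight of the point, but the contradiction remains.

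**Conclusion.** The concern holds. As written, the primary power model ignores the repeated-measures design, and 4.3.1.5 gives an incompatible instruction without saying which prevails.

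Under level differences only, the literal nominal 90% interval covers about 93% to 99% for ICC 0.3 to 0.9. With 12 completers it is 1.06 to 2.75 times as wide as a within-subject interval; at ICC 0 to 0.1 there is little harm. The direction depends on equal slopes, since slope differences reduce or reverse the over-coverage. ICC and slope variance are assumptions, because the documents give neither. With slope variance set as a multiple of σ², coverage and width ratios do not depend on the value of σ².

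The point estimate is unbiased on the literal reading. The effect is confined to the precision and calibration of a secondary PK interval, so this is a change that should be made, not one that threatens the study.

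**What to change.** **SAP 4.3.1.3, power model:** fit log(Y) on log(dose) with subject as a random effect and Kenward-Roger degrees of freedom, matching the supportive ANOVA, and replace the reference to a pooled variance accordingly.

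**SAP 4.3.1.5:** add that the REPEATED type=UN instruction is not added to the power model's random subject.

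Because a random intercept can under-cover if slopes vary between subjects, the interval should be read with that limit in mind. Tidying the covariance bullets for the ANOVA and accumulation models is optional; no effect on their results has been shown.

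Cost: one sentence in each section, with no extra data or assessments.

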4.3.1.4. Accumulation Assessment

The assessment of accumulation will be performed following repeated dosing of GSK3923868 in Period 3 only.

Pharmacokinetic Statistical Analyses
Endpoint(s)

 • AUC(0-6), Cmax on Day 14 compared to Day 1 • Each endpoint to be assessed separately following a log-transformation.
Model Specification

 • A mixed effect model will be fitted with day as a fixed effect and subject as a random effect. • The Kenward & Roger (KR) degrees of freedom approach will be used. • Day 14 will be compared to Day 1 in order to estimate the accumulation ratio(s) • The accumulation ratio(s) and 90% confidence interval will be calculated by back-transforming the difference between the least square means for the two days and associated 90% confidence interval.
Model Results Presentation

 • Point estimates and confidence intervals for the ratios will be reported to 2 decimal places • Scatter plots of each endpoint against day will be produced. The data points for each subject will be joined with straight lines • Boxplots of each endpoint against day will be produced. Each endpoint will be put on a separate page.

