9.4.3. Secondary Endpoint Analysis

All pharmacokinetic analyses will be performed on the PK Population.

Pharmacokinetic analysis will be the responsibility of the CPMS department within GlaxoSmithKline.

Plasma GSK3923868 concentration-time data will be analyzed by non-compartmental methods with WinNonlin. Calculations will be based on the actual sampling times recorded during the study.

From the plasma concentration-time data, the following pharmacokinetic parameters will be determined if data permitting, for each dose of GSK3923868:

- Treatment period 1 & 2 (single ascending doses): AUC(0-t), AUC(0-24), Cmax and Tmax
- Treatment period 3 (repeat dose): Cmax, Tmax and AUC(0-6) on Day 1 and Day 14

Pharmacokinetic data will be presented in graphical and/or tabular form and will be summarised descriptively. Analysis of dose proportionality and dose accumulation following repeated dosing (period 3 only) will be conducted. A population PK model (POP PK) may be developed with all available data from this and historical studies as appropriate and will be reported separately. Further details of the analysis plan and methods will be defined within the SAP.

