1.1. Objectives and Endpoints

Objectives	Endpoints
Primary	

 To assess the safety and tolerability of GSK3923868 following single and repeat inhaled administration in participants with Chronic Obstructive Pulmonary Disease (COPD). 	
 Occurrence of adverse events (AEs) and serious adverse events (SAEs). Clinically significant changes in laboratory values, vital signs, 12-lead electrocardiogram (ECG) and spirometry measurements up to Follow Up.
Secondary	

 To evaluate the plasma pharmacokinetics of GSK3923868 following single and repeat inhaled administration in participants with COPD. 	
Derived pharmacokinetic parameters as data permit, including (but not limited to):
 
 Area under the plasma-concentration time curve (AUC): area under the concentration-time curve from time 0 (pre-dose) to 24 hours post dose administration following the first dose (AUC[0-24]) or area under the concentration-time curve from time 0 to the time of the last quantifiable concentration (AUC[0-t]) for single dose and area under the concentration-time curve from time 0 (pre-dose) to 6 hours post dose administration following the first dose (AUC[0-6]) for repeat dose Maximum observed plasma drug concentration (C_{max}), time to maximum observed plasma drug concentration (T_{max})

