4.3. Secondary Endpoint(s) Analyses

All pharmacokinetic analyses will be performed on the PK Population.

For PK endpoints, all analysis will be performed by Part i.e., Part A (Periods 1 and 2, single dose) and Part B (Period 3, repeat dose), except dose proportionality, which will be carried out using data from the three periods.

From the plasma concentration-time data, the following pharmacokinetic parameters will be determined if data permitting, for each dose of GSK3923868:

- Treatment period 1 & 2 (single ascending doses): AUC(0-t), AUC(0-24), AUC(0-6), Cmax and Tmax
- Treatment period 3 (repeat dose): Cmax, Tmax and AUC(0-6) on Day 1 and Day 14

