4.3.1. Key secondary endpoint(s)

4.3.1.1. Definition of endpoints

Parameter	Parameter Description
AUC(0-t)	Area under the concentration-time curve from time zero to the time of the last quantifiable concentration (C(t)) will be calculated using the linear trapezoidal rule for each incremental trapezoid and the log trapezoidal rule for each decremental trapezoid.
AUC (0-24)	Area under the concentration-time curve over the dosing interval.
Cmax	Maximum observed concentration, determined directly from the concentration-time data over the dosing interval.
Tmax	Time to reach Cmax, determined directly from the concentration-time data over the dosing interval/
AUC (0-6)	Area under the concentration-time curve from time 0 to 6-hour post dose.

NOTE: Additional parameters may be included as required.

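### The accumulation ratio compares a Day 14 AUC(0-6) without a 4 h sample with a Day 1 AUC(0-6) that has one; a common time grid removes a small, mostly upward error

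*SAP*

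**What the plan says.** SAP 4.3.1.4 compares "AUC(0-6), Cmax on Day 14 compared to Day 1" in a mixed model on the log scale, with day as fixed effect and subject as random effect. The back-transformed difference is the accumulation ratio, reported with a 90% confidence interval to two decimals. SAP 4.3 lists the inputs: "Treatment period 3 (repeat dose): Cmax, Tmax and AUC(0-6) on Day 1 and Day 14".

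The Period 3 schedule in Protocol 1.3.3 has these PK times:

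| Day | PK samples |
|---|---|
| Day 1 | pre-dose, 5, 15, 30, 45 min, 1, 2, **4**, 6 h |
| Day 14 | pre-dose, 5, 15, 30, 45 min, 1, 2, 6 h |

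SAP 4.3.1.1 gives an integration rule for AUC(0-t), the "linear trapezoidal rule for each incremental trapezoid and the log trapezoidal rule for each decremental trapezoid". The AUC(0-6) row says only "Area under the concentration-time curve from time 0 to 6-hour post dose".

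Dose proportionality is a separate analysis: "The assessment of dose proportionality will utilise Period 1,2 and the first dose of Period 3 data only". Periods 1 and 2 and Period 3 Day 1 all include the 4 h sample.

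**The concern.** A ratio of two areas isolates accumulation only if both areas are measured in the same way. Here the denominator has a sample in the middle of the 2 to 6 h stretch and the numerator does not. A log trapezoid is exact for a single exponential. If the decline flattens on the log scale, as it does with a fast and then a slow phase, the straight log-scale line from 2 h to 6 h lies above the true curve. The wider the interval, the larger the excess, so the Day 14 area is overstated more than the Day 1 area. The result resembles mild accumulation, and because the error is systematic the confidence interval does not reveal it.

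At stake is the accuracy of one modelled secondary result. No dosing decision depends on it: Protocol 6.5.2 and 7.1.5 set no PK criteria for dose modification or stopping, and no formal hypothesis is tested.

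**Working it through.** The plan gives no sample size or precision figure for the accumulation ratio, so there is none to reproduce.

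**1. Grids.** Both pages of the Period 3 table show a 4 h column under Day 1 and none under Day 14. The PK row carries 8 post-dose marks on Day 1 and 7 on Day 14. The marks do not align perfectly with the columns in the text version, but the headers and the count agree.

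**2. Rule.** Rising step: (c0 + c1)/2 × Δt. Falling step: (c0 − c1) × Δt / ln(c0/c1). This is the rule stated for AUC(0-t). The last planned sample on either day is at 6 h, so when that sample is quantifiable AUC(0-t) and AUC(0-6) use the same trapezoids.

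**3. One profile in full (assumed).** Absorption rate 12/h; 90% of amplitude with half-life 1 h and 10% with half-life 6 h:

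C(t) = 0.9 × (e^(−0.693t) − e^(−12t)) + 0.1 × (e^(−0.1155t) − e^(−12t))

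Day 14 is the sum of 14 doses 24 h apart.

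| | Day 1 | Day 14 |
|---|---|---|
| C at 2, 4, 6 h | 0.3044, 0.1192, 0.0641 | 0.3097, not sampled, 0.0674 |
| Area 0–2 h | 1.0562 | 1.0681 |
| Area 2–6 h, two trapezoids | 0.3951 + 0.1776 = 0.5727 | – |
| Area 2–6 h, one trapezoid | 0.6168 | 0.6355 |
| True area 2–6 h | 0.5586 | 0.5755 |
| True area 0–6 h | 1.6276 | 1.6565 |

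- Planned ratio: (1.0681 + 0.6355) / (1.0562 + 0.5727) = 1.7036 / 1.6289 = **1.046**
- Common grid: 1.7036 / (1.0562 + 0.6168) = 1.7036 / 1.6730 = **1.018**
- True ratio: 1.6565 / 1.6276 = **1.018**

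To two decimals the plan would report 1.05 where 1.02 is right. On the common grid the overstatement of 2–6 h occurs on both days and cancels.

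**4. Range of assumed profiles.** Two-phase set: absorption rate 6, 12, 20 per h; fast half-life 0.5, 1, 2 h; slow half-life 3, 6, 12, 24 h; slow amplitude 5, 10, 20%. That is 3 × 3 × 4 × 3 = 108 profiles. Error against the true ratio, linear-up/log-down:

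| Set | Planned grids | Common grid |
|---|---|---|
| Mono-exponential, half-life 1, 1.5, 2 h (9) | 0% | – |
| Two-phase (108) | +0.04% to +4.7%, median +2.2% | −1.4% to +0.9% |
| Slower absorption, 1.5 to 3 per h (96) | −1.1% to +5.4% | −2.1% to +1.0% |

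The common grid is closer to the truth in 107 of the 108 two-phase profiles and in 91 of the 96 slower-absorption profiles. The third row shows that the direction is usually, but not always, upward.

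**5. Size beside the confidence interval.** Protocol Table 1 gives three sequences of 3 on active drug in Period 3, so n = 9; Protocol 9.2 also considers n = 6. Half-width on the log scale: h = t(0.95, n − 1) × √(2 × ln(1 + CV²)/n), with within-subject CV assumed. With t = 1.860 at n = 9 and 2.015 at n = 6:

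| CV | h (n = 9) | 90% CI multipliers, n = 9 | multipliers, n = 6 | ln(1.047)/h, n = 9 |
|---|---|---|---|---|
| 15% | 0.131 | 0.88–1.14 | 0.84–1.19 | 0.046/0.131 = 0.35 |
| 25% | 0.216 | 0.81–1.24 | 0.75–1.33 | 0.046/0.216 = 0.21 |
| 40% | 0.338 | 0.71–1.40 | 0.64–1.57 | 0.046/0.338 = 0.14 |

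**The case against.** The strongest reply is that this is small and unproven for this drug. No half-life is given, the effect vanishes under mono-exponential decline, and even the worst two-phase case is about a third or less of the interval half-width at n = 9. All of that stands and sets the severity. What remains is that the error is systematic, usually in one direction, and avoidable with samples already planned. Protocol 8.4 allows up to three extra samples and changes of timing, but nothing commits one to 4 h on Day 14.

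Three stronger readings are tempting, and the documents do not support them.

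- *The error could reach about 10%.* That needs an all-linear trapezoidal rule, which neither document states. The only rule given is linear-up/log-down, and its silence in the AUC(0-6) row is missing detail.
- *The repeat-dose endpoint is Day 1 only.* SAP 1.1 does word it as "to 6 hours post dose administration following the first dose (AUC[0-6]) for repeat dose", as does the protocol synopsis. But Protocol 9.4.3, SAP 4.3 and SAP 4.3.1.4 all name both days. This is an editorial slip.
- *Single-dose AUC(0-24) is a failed endpoint.* It is listed ("Treatment period 1 & 2 (single ascending doses): AUC(0-t), AUC(0-24), AUC(0-6), Cmax and Tmax"; Protocol 9.4.3 likewise), and sampling in Periods 1 and 2 stops at 6 h, so it cannot be observed there. But both documents make it conditional on the data and offer AUC(0-t) as the alternative, and no model uses it. Its two descriptions in the SAP, 24 h and the dosing interval, agree under once-daily dosing.

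**Conclusion.** The point holds as a minor one. The accumulation ratio is planned on unequal time grids, and matching them is a cheap improvement. Under linear-up/log-down the resulting error is nil for mono-exponential decline and +0.04% to +4.7% (median about +2%) over the 108 assumed two-phase profiles. At its largest it is 14% to 35% of the 90% interval half-width at n = 9 for CV 40% to 15%. Profile shapes and CVs are assumptions; only the grids, the stated rule and the sample sizes come from the documents. A reader might infer that the accumulation result would be invalid, or that bias has been shown for GSK3923868. Neither follows. Dose proportionality is unaffected, because all three periods share the 4 h sample there.

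**What to change.** Change the SAP only.

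1. In 4.3.1.4, compute the AUC(0-6) accumulation ratio from the times scheduled on both days: pre-dose, 5, 15, 30 and 45 min, 1, 2 and 6 h. Report the ratio that uses the full Day 1 grid beside it. At minimum, add the common-grid ratio as a sensitivity analysis.
2. In 4.3.1.1, state that linear-up/log-down applies to AUC(0-6) as well.
3. In 4.3.1.3, keep the full-grid Day 1 AUC(0-6) for dose proportionality.

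Add no new exclusion for a non-quantifiable 6 h sample; handle it as in the planned analysis. Such an exclusion would shrink a group of 9 and would drop participants who are non-quantifiable at 6 h on Day 1 but quantifiable on Day 14, the ones with the most apparent accumulation.

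The cost is one fewer Day 1 point in the ratio and two Day 1 AUC(0-6) values to label by use. With an assumed 10% random error per concentration, the SD of an individual log ratio goes from 0.054–0.068 to 0.055–0.073; with 15%, from 0.082–0.101 to 0.085–0.109. No sample, visit or protocol amendment is needed.

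As editorial notes for the next revision: align the repeat-dose AUC(0-6) wording with Day 1 and Day 14, and note that single-dose AUC(0-24) cannot be observed from sampling to 6 h. The AUC(0-24) row need not be deleted. Footnote 6 of Protocol 1.3.3 lets the Day 14 pre-dose sample serve as the 24 h value after the Day 13 dose, and that provision could use the definition.
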